11 OTHER ANALYSES

11.1 Dose change in use of concomitant medications over time

The following summaries will be produced using SS in all participants:

- The number and percentage of participants with dose change in use of steroids (ATC3 code: █████), immunosuppressants (ATC3 code: █████) or AChE Inhibitor (ATC3 code: █████) during the study;
- Average daily dose (ADD) by PT of medications at Baseline and last study visit (i.e. PEOT/EOS visit);

Note: ADD will be calculated for each PT according to the dose and dose frequency on Prior and Concomitant Medications CRF (e.g. ADD of a participant taking steroid 20 mg QOD is 10 mg). Baseline ADD will follow the same Baseline definition in [Section 3.3](#), which will be calculated using the steroid dose taken prior to first IMP in MG0004. ADD at last study visit is calculated using the dose taken at EOS/PEOT visit. In the case last dose is stopped before EOS/PEOT visit, ADD at last study visit will be counted as zero.

- The change from Baseline of average daily dose (ADD) at last study visit, calculated as
ADD at last study visit – Baseline ADD;
- A listing will be provided for participants with dose change of steroids, including MG-ADL total score at Baseline and last study visit (EOS/PEOT visit), last MG-ADL score prior to first steroid dose change, maintenance dose of RLZ, Baseline steroid ADD and steroid ADD at last study visit.

Note: Maintenance dose of RLZ is the most recent dose of RLZ when last steroid dose is given.

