	
• Change from Baseline in the MG Symptoms PRO ‘Muscle Weakness Fatigability’ score at each scheduled assessment during Treatment and Observation Periods• Change from Baseline in the MG Symptoms PRO ‘Physical Fatigue’ score at each scheduled assessment during Treatment and Observation Periods• Change from Baseline in the MG Symptoms PRO ‘Bulbar symptoms’ score at each scheduled assessment during Treatment and Observation Periods• Change from Baseline in the MG Symptoms PRO ‘Respiratory symptoms’ score at each scheduled assessment during Treatment and Observation Periods• Change from Baseline in the MG Symptoms PRO ‘Ocular symptoms’ score at each scheduled assessment during Treatment and Observation Periods• Change from Baseline in the MG Symptoms PRO multicomponent total score, at each scheduled assessment during Treatment and Observation Periods• Change from Baseline in the enhanced MG Symptoms PRO total score, at each scheduled assessment during Treatment and Observation Periods• Change from Baseline in MGQoL15r at each scheduled assessment during Treatment and Observation Periods• Change from Baseline in EQ-5D-5L scores at each scheduled assessment during Treatment and Observation Periods 
For study participants who require rescue treatment during the Observation Period of MG0003 and subsequently enter MG0004, the following endpoints will be assessed:
 
• QMG responder rate (≥ 3.0 point improvement from Baseline) at each scheduled assessment during the first 6 weeks of the Treatment Period• MG-C responder rate (≥ 5.0 point improvement from Baseline) at each
--	--

	
scheduled assessment during the first 6 weeks of the Treatment Period
 
 • MG-ADL responder rate (≥ 2.0 point improvement from Baseline) at each scheduled assessment during the first 6 weeks of the Treatment Period
Other	
To assess the reduction in use of steroids in study participants receiving rozanolixizumab	
 • AUC of the oral steroid dose over time
To assess the plasma concentrations of rozanolixizumab administered by SC infusion	
 • Plasma concentration of rozanolixizumab at each scheduled assessment during the Treatment and Observation Periods

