2.1.3 Other objectives

- To assess the dose change in use of concomitant medications in study participants receiving rozanolixizumab
- To assess the plasma concentrations of rozanolixizumab administered by subcutaneous (sc) infusion
- To assess the pharmacodynamic effects of rozanolixizumab as measured by IgG levels, IgG subclasses and MG-specific autoantibodies levels
- To evaluate the incidence and emergence of anti-drug antibodies (ADAs) with respect to immunogenicity, pharmacokinetic (PK), and pharmacodynamics
- To assess the effect of rozanolixizumab on biomarkers including IgM, IgA, and IgE, serum and plasma complement levels, and serum cytokines
- To assess the effect of rozanolixizumab on tetanus IgG antibodies

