3.9 Changes to protocol-defined analyses

- The following two exploratory endpoints will not be analyzed as they have been removed from the MG program as a whole and have been included in the protocol in error:
 - Change from Baseline in the MG Symptoms PRO multicomponent total score, at each scheduled assessment during Treatment and Observation Periods,
 - Change from Baseline in the enhanced MG Symptoms PRO total score, at each scheduled assessment during Treatment and Observation Periods.
- The increase or reduction in use of concomitant medications will be analyzed in the SAP, so objective is changed to “To assess the dose change in use of concomitant medications in study participants receiving rozanolixizumab” in the SAP.

- The dose change in use of concomitant medications in study participants receiving rozanolixizumab will be analyzed using number and percentage of participants with dose change of concomitant medications and change from Baseline in ADD in the study. There is no concentration data of concomitant medications in the study to generate area under the curve (AUC), so it is not included in the SAP.
- No study participants from MGC003 will rollover into MG0004. Thus, the maximum sample size of this study should be 240, not 276.

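### SAP 11.1 counts any change in steroid dose without direction, so no planned summary gives the number who reduced steroids and the number who increased them

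*SAP*

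**What the plan says.** Protocol Section 3 lists among its Other objectives "To assess the reduction in use of steroids in study participants receiving rozanolixizumab", with the endpoint "AUC of the oral steroid dose over time".

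SAP 3.9 changes this in the open. It states that "The increase or reduction in use of concomitant medications will be analyzed in the SAP", and the objective in SAP 2.1.3 becomes "To assess the dose change in use of concomitant medications in study participants receiving rozanolixizumab". The AUC endpoint is dropped, and the objective is to be analyzed "using number and percentage of participants with dose change of concomitant medications and change from Baseline in ADD in the study".

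SAP 11.1 carries this out in the Safety Set, in all participants:

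- The first summary is "The number and percentage of participants with dose change in use of steroids", immunosuppressants or AChE inhibitors during the study. It has no split by direction and no reference to Baseline dose or Baseline use. It does not say whether a new start counts, or whether the three classes are counted separately or together.
- ADD is summarized by preferred term at Baseline and at the last study visit. A drug stopped before that visit has a last-visit ADD of zero.
- The change in ADD is the last-visit value minus the Baseline value.
- Participants with a steroid dose change are listed with Baseline and last-visit steroid ADD and MG-ADL scores.

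SAP 6.4 adds a by-participant listing for all three classes, with ADD at both times and its change.

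**The concern.** Both versions of the objective are about direction: the protocol asks about reduction, and SAP 3.9 promises increase or reduction. The count in SAP 11.1 cannot show either. A sustained taper, an escalation for worsening disease and a short temporary course each put one participant in the numerator. All three can occur, because Protocol 6.5.1 allows dose adjustments of MG medication and sets no dose requirement for oral corticosteroids.

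Nothing in this study is tested, so the descriptive tables are the evidence. A dose-change percentage, placed where the protocol had a steroid-reduction objective, could be taken as a sign of steroid sparing. Yet it also rises when more participants need more steroid.

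**Working it through.** No design figure lies behind this point, so there is nothing in the plan to reproduce beyond its ADD example: 20 mg every other day gives 20/2 = 10 mg/day, as SAP 11.1 states. The check applies the section's own definitions to assumed data.

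**1. The count.** Any change % = decrease only % + increase only % + both %. With nobody in the last category:

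- 25% taper and 10% escalate: 25 + 10 + 0 = 35%.
- 10% taper and 25% escalate: 10 + 25 + 0 = 35%.

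**2. Count and signed ADD change together.** Assume ten steroid users on one preferred term. Each moves between 20 and 10 mg/day and stays there to the last visit. Change = last-visit ADD − Baseline ADD, so a taper is −10 mg and an escalation is +10 mg.

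| Assumed group | Any change (planned) | Mean ADD change (planned) | Decreased (not planned) | Increased (not planned) |
|---|---|---|---|---|
| All 10 taper | 100% | 10×(−10)/10 = −10 mg | 100% | 0% |
| All 10 escalate | 100% | 10×(+10)/10 = +10 mg | 0% | 100% |
| 5 taper, 5 escalate | 100% | (−50+50)/10 = 0 mg | 50% | 50% |
| 8 taper, 2 escalate | 100% | (−80+20)/10 = −6 mg | 80% | 20% |

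The planned count is the same in every row. The signed mean gives net direction. The split columns give the number in each direction, and no planned summary supplies them.

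**3. Why the ADD summaries do not replace the count.**

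- *Cancellation.* In the third row the mean is 0 mg although everyone changed. SAP 3.1 also provides SD, median, minimum and maximum. Here the minimum is −10 and the maximum +10, which shows that both directions occurred. The fourth row has the same minimum and maximum with an 80/20 split, so the extremes do not give the number of reducers.
- *Two time points.* A participant who goes from 10 to 20 mg/day and back to 10 before the last visit has an ADD change of 10 − 10 = 0 but is in the dose-change count. The two summaries can therefore describe different participants.
- *Preferred term.* A participant who moves from 10 mg/day of one steroid to 10 mg/day of another contributes 0 − 10 = −10 mg under the first term. If Baseline ADD of the second is taken as zero, the participant contributes 10 − 0 = +10 mg under that term. The section does not say how such a switch enters the count.

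**4. The denominator.** The section uses all Safety Set participants. Someone not on a class at Baseline cannot reduce it, so a reduction percentage on that base would be diluted by non-users.

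**The case against.** The strongest reply is that the plan says what it is doing and does not conceal direction. Most of that stands.

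- *A reader might infer an unacknowledged mismatch between protocol and SAP.* The documents do not support that. SAP 3.9 declares the new objective and names both replacement measures, and SAP 2.1.3 and 2.2.6 agree with it. Nor did the protocol plan a proportion who reduced steroids; its endpoint was a dose AUC. The split is an added summary, not the return of a dropped one.
- *A reader might infer that direction is lost from the analysis.* It is not. The ADD change is signed and comes with its full set of descriptive statistics, and the listings in SAP 6.4 and 11.1 show who ended lower or higher.
- *A reader might say the percentage overstates a reduction rate.* The SAP calls it dose change throughout and never a reduction or steroid-sparing rate, so it makes no such claim. With equal steps, the ADD change would also separate the two 35% profiles by sign: 0.25×(−10) + 0.10×(+10) = −1.5 mg against 0.10×(−10) + 0.25×(+10) = +1.5 mg.

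The SAP also refers to separate table shells, which are not among the documents. Given the wording of SAP 3.9, a split could appear there; this cannot be checked.

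What remains is narrower. Listings must be counted by hand and are not a summary. The SAP text, which should govern the shells, specifies no count by direction although its own objective covers increase and reduction.

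**Conclusion.** The point holds as a gap in presentation. As written, the first summary in SAP 11.1 merges decreases and increases, and no summary in the SAP gives the number or percentage who reduced against those who increased steroids. The same applies to immunosuppressants and AChE inhibitors.

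The size cannot be fixed from the documents, which give no rates of steroid change. The 35% profiles and the ten-participant groups are assumptions; they show only that the count does not respond to direction. The conclusion rests on the SAP text alone and would fall away if the shells already contain the split.

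The stakes are low. This is an Other objective, all analyses are descriptive, no test is planned, and no formal conclusion depends on the figure. It is worth correcting because the correction is cheap and lets the section answer the objective it sets itself.

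**What to change.** In SAP 11.1, replace the first bullet with n (%) in mutually exclusive rows, relative to Baseline dose:

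- decreased only, including stopped;
- increased only;
- both directions during the study;
- no change.

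Report these separately for steroids, immunosuppressants and AChE inhibitors, with participants on that class at Baseline as the denominator. Add a row for newly started, among those not on the class at Baseline.

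State how a switch between preferred terms within a class is classified, for example in a separate switched row or, for steroids, by a prespecified dose-equivalence conversion. Without such a rule, class-level direction is undefined for these participants. Keep the ADD summaries and listings as they are.

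The cost is SAP wording, a small classification rule and one reprogrammed table. Dose and frequency are already on the Prior and Concomitant Medications CRF, so no new data are needed.

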	
• Change from Baseline in the MG Symptoms PRO ‘Muscle Weakness Fatigability’ score at each scheduled assessment during Treatment and Observation Periods• Change from Baseline in the MG Symptoms PRO ‘Physical Fatigue’ score at each scheduled assessment during Treatment and Observation Periods• Change from Baseline in the MG Symptoms PRO ‘Bulbar symptoms’ score at each scheduled assessment during Treatment and Observation Periods• Change from Baseline in the MG Symptoms PRO ‘Respiratory symptoms’ score at each scheduled assessment during Treatment and Observation Periods• Change from Baseline in the MG Symptoms PRO ‘Ocular symptoms’ score at each scheduled assessment during Treatment and Observation Periods• Change from Baseline in the MG Symptoms PRO multicomponent total score, at each scheduled assessment during Treatment and Observation Periods• Change from Baseline in the enhanced MG Symptoms PRO total score, at each scheduled assessment during Treatment and Observation Periods• Change from Baseline in MGQoL15r at each scheduled assessment during Treatment and Observation Periods• Change from Baseline in EQ-5D-5L scores at each scheduled assessment during Treatment and Observation Periods 
For study participants who require rescue treatment during the Observation Period of MG0003 and subsequently enter MG0004, the following endpoints will be assessed:
 
• QMG responder rate (≥ 3.0 point improvement from Baseline) at each scheduled assessment during the first 6 weeks of the Treatment Period• MG-C responder rate (≥ 5.0 point improvement from Baseline) at each
--	--

	
scheduled assessment during the first 6 weeks of the Treatment Period
 
 • MG-ADL responder rate (≥ 2.0 point improvement from Baseline) at each scheduled assessment during the first 6 weeks of the Treatment Period
Other	
To assess the reduction in use of steroids in study participants receiving rozanolixizumab	
 • AUC of the oral steroid dose over time
To assess the plasma concentrations of rozanolixizumab administered by SC infusion	
 • Plasma concentration of rozanolixizumab at each scheduled assessment during the Treatment and Observation Periods

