already started MG0004, a minimum treatment duration of 6 visits must be completed (if IMP treatment is withheld for low IgG, study participants missed dose(s) can be counted as part of the total 6 visits for completion of MG0004 and meet eligibility requirements for MG0007) and then the participant will discontinue MG0004 and have the opportunity to enter into MG0007. For study participants entering MG0007 from the treatment period of MG0004, he/she must complete the PEOT Visit in MG0004 which will serve both as the Screening Visit for MG0007 and as the EOS for MG0004. If a study participant completes the Treatment Period and is in the Observation Period of MG0004, he/she will then complete the EOS visit to serve as the Screening Visit for MG0007. Once the site is active for MG0007, no further participants will enroll in MG0004 and the study will be closed at the site once all eligible study participants have rolled over into MG0007.

An IDMC will be formed to monitor the ongoing safety of the study. The IDMC will review implications of individual and cumulative cases to continuance of the study in an ongoing fashion.

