MG0004 will then evaluate the long-term safety, tolerability, and efficacy of rozanolixizumab over a 52-week Treatment Period. An open-label study with a treatment duration of 52 weeks is considered sufficient to adequately assess long-term safety with rozanolixizumab for the proposed indication. The dose regimen for rozanolixizumab in MG0004 will be the same one that is used in MG0003 and MGC003 (equivalent to approximately [REDACTED]), although the dose may be modified based on interim analysis in MG0003 (Section 4.3). In MG0004, study participants will be rerandomized to 1 of 2 doses of rozanolixizumab, and will be allowed to switch between dose arms at the discretion of the Investigator. MG0004 will therefore allow study participants to switch their dose of study medication on an individual basis. MG0004 also offers study participants the chance to benefit from long-term treatment. MG0004

will conclude with an 8-week Observation Period, which is the anticipated duration of time required for antibodies to return to Baseline levels after rozanolixizumab treatment.

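### SAP 11.1 measures steroid dose change by preferred term and only at the last visit, so it mixes on-drug with washed-out doses and gives no net change per participant

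*SAP*

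**What the plan says.** The protocol (section 3, Objectives and Endpoints) lists as an other objective: "To assess the reduction in use of steroids in study participants receiving rozanolixizumab". Its endpoint is the area under the curve of oral steroid dose over time. SAP 3.9 drops that endpoint, and SAP 2.1.3 restates the objective as dose change in concomitant medications, still in participants receiving rozanolixizumab.

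SAP 11.1 sets the replacement rules:

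- **Level and unit.** "ADD will be calculated for each PT according to the dose and dose frequency on Prior and Concomitant Medications CRF", with the worked case "e.g. ADD of a participant taking steroid 20 mg QOD is 10 mg". No conversion to a common steroid equivalent is stated, and no sum across PTs.
- **Baseline.** It is the dose "which will be calculated using the steroid dose taken prior to first IMP in MG0004". No value is given for a PT first started later.
- **Follow-up.** The only follow-up time point is the last study visit, meaning PEOT or EOS. Week 52 is not named.
- **Stopped drug.** "In the case last dose is stopped before EOS/PEOT visit, ADD at last study visit will be counted as zero".

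The same section also counts participants with any dose change by drug class during the study. It asks for a listing of steroid ADD at Baseline and at the last visit.

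On timing, protocol 4.4 puts EOS at Week 60. Protocol 4.2 describes the 8-week Observation Period as one "which is the anticipated duration of time required for antibodies to return to Baseline levels after rozanolixizumab treatment". Under protocol 4.1, a participant who goes to MG0007 from the Treatment Period must "complete the PEOT Visit in MG0004 which will serve both as the Screening Visit for MG0007 and as the EOS for MG0004". Under protocol 7.2, a participant who stops study medication early has a PEOT visit and then enters the Observation Period.

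**The concern.** With the dose AUC removed, the ADD change is the only planned summary that gives the size and direction of steroid change. Protocol 6.5.1 lets background doses move during the study, so its rules will be used. Two of them work against the question asked.

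First, the follow-up value is taken at different points relative to rozanolixizumab. It comes after washout in completers and at or near the end of dosing in Treatment Period transfers. For participants who stop early and have both PEOT and EOS, the SAP does not say which visit counts. A steroid dose raised during the Observation Period would be charged to treatment in completers and never seen in transfers. The pooled mean would then depend on when sites opened MG0007.

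Second, a by-PT change in raw mg has no participant-level total. When one steroid replaces another, the stopped PT falls to zero, and the SAP gives no matching Baseline for the started PT. Steroid sparing is a claim about a participant's total steroid load, and that quantity is not obtained.

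**Working it through.** **1. The plan's own figure.** ADD = dose / dosing interval in days = 20 / 2 = 10 mg/day. This reproduces the SAP 11.1 example.

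**2. Timing.** Treatment Period 52 weeks, Observation Period 8 weeks: 52 + 8 = 60. EOS is therefore 60 - 52 = 8 weeks after the end of treatment. The last visit then depends on how the participant leaves:

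| Participant | Last study visit in SAP 11.1 | State |
|---|---|---|
| Completer | EOS, Week 60 | after washout |
| Transfer to MG0007 from the Treatment Period | PEOT | at or near end of dosing |
| Transfer to MG0007 from the Observation Period | EOS | off drug |
| Early stop without transfer | PEOT, then Observation Period | not specified which visit is used |

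**3. One completer (assumed doses).** Baseline 20 mg/day, tapered to 5 mg/day by Week 52. The change on drug is 5 - 20 = -15 mg. If the dose at Week 60 lies between 5 and 25 mg/day, the SAP change is between 5 - 20 = -15 mg and 25 - 20 = +5 mg. The -15 mg at Week 52 appears in no planned ADD summary.

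**4. Pooling (assumed changes).** Let f be the share measured at PEOT with a change of -15 mg, and d the change at EOS in the rest. Mean = f x (-15) + (1 - f) x d.

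| EOS change d | f = 25% | f = 50% | f = 75% |
|---|---|---|---|
| -15 mg | -15.0 | -15.0 | -15.0 |
| 0 mg | -3.75 | -7.5 | -11.25 |
| +5 mg | 0.0 | -5.0 | -10.0 |

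The mix is harmless only if doses do not move after treatment ends (first row).

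**5. A switch (assumed doses).** Steroid A at 20 mg/day is replaced by an equipotent dose of steroid B, 20r mg/day. The documents give no equivalence factors, so r is taken from 0.5 to 2.

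- Row of A: 0 - 20 = -20 mg, whatever r is.
- Row of B: no value if Baseline is missing; +20r = +10 to +40 mg if Baseline is set to 0.
- Raw-mg sum of A and B, with B's Baseline at 0: 20r - 20 = -10 to +20 mg.
- Sum in A-equivalents: 20r/r - 20 = 0 for every r.

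**6. Effect on one PT's mean (assumed counts).** If k of 40 users of A switch and nobody else changes, the mean change in A's row is -20k/40. This is -1.0 mg for k = 2, -2.5 mg for k = 5 and -5.0 mg for k = 10, with no true change in steroid use.

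**The case against.** The best defence is scope. SAP 2.2.6 defines the dose-change endpoint over both the Treatment and Observation Periods, and SAP 3.9 openly records the departure from the protocol. A value at the last visit is inside that scope, so leaving out Week 52 is a reporting gap and not a contradiction. That much stands. It does not remove the problem: the restated objective still concerns participants receiving the drug, and a two-period scope is better served by reporting each period than by one pooled value.

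The zero rule is also right when a steroid is truly stopped, and no rule excludes newly started drugs. A reader might infer that the SAP counts a swap as an overall steroid reduction. The documents support this only for the stopped PT's row. The started PT's row is an increase or blank, depending on a Baseline convention that the SAP leaves open, and a raw-mg total could move either way.

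A reader might also infer that the on-drug change is not measured at all. That goes too far. Treatment Period transfers are measured at PEOT, and the count of participants with a dose change covers the whole study, though without size or direction.

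Two further points have some force. By-participant listings (SAP 6.4 and 11.1) let stops and starts be inspected, but they too lack a rule for combining PTs. And the documents give no evidence of how often steroids are switched; protocol Table 6-2 names only prednisolone.

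**Conclusion.** The point holds, limited to this: the planned ADD change pools on-drug and off-drug doses, provides no on-drug change for completers, and cannot yield net steroid change per participant. Following the text exactly gives a less useful answer than the data allow.

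The timing part rests on the documents' own schedule. Its numerical size does not. The 11.25 - 3.75 = 7.5 mg spread in the pooled mean assumes a full return to Baseline dose by Week 60 and PEOT shares of 25% to 75%. It vanishes if doses stay put after treatment. The switch illustration likewise rests on assumed doses and counts, and it describes one PT's row, not steroid use overall.

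The consequence is limited. This is a descriptive other endpoint, and SAP 4.1 plans no testing, so no test, sample size or primary or secondary result is affected. The change should still be made before any steroid-sparing statement is drawn from this table.

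**What to change.** Amend SAP 11.1 as follows:

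1. Report the steroid ADD change at the end of treatment (Week 52 or PEOT) for everyone. Show EOS separately, labelled as an off-treatment value. This also settles which visit applies when a participant has both.
2. Add one class-level oral corticosteroid ADD per participant, in a declared common equivalent from a named conversion table, summed across PTs. Use 0 at Baseline or follow-up when none is taken.
3. Use this class-level value wherever the listings call for a steroid ADD. Keep the by-PT table as supportive.

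The cost is SAP wording, a conversion table and programming. No new data are needed: the protocol's Schedule of Activities records concomitant medications at every visit, including Week 52, and SAP 11.1 already takes dose and frequency from the CRF.
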